13.3.1 Qualitative Data Analysis

All interview data (from patients, PCPs and leaders) will be analyzed in two phases by a team consisting of the interviewers and analysts from each of the sites:

1. Small samples will be reviewed immediately without coding to identify specific intervention problems needing prompt attention and revision in implementation approach.
2. As larger samples are created, we will use a more standard content analysis employing an iterative data-reduction method.[56]

A draft codebook will be developed based on the structure and content of the interview guide. That will be revised during application in early interviews by the analysis group so that eventually

coding can be performed by pairs of analysts while the larger analytic group can focus on the identification of categories, themes, and patterns emerging from the data. The main analytic purpose is to identify the clinic, PCP and patient barriers and facilitators to consistent effective use of the OUD-CDS.[57] Classification schemes and typologies will be used to identify and develop themes, concepts, and patterns. Coding and managing qualitative analyses will be conducted using appropriate software.

We will maintain a data codebook and audit trail in order to map decision points in the analysis. Individual interviews that do not fit evolving patterns in the data will get special attention. The analysis team will work to agree on final themes and patterns in the data and interview data will be triangulated with other data sources. These themes and patterns will then be developed into recommendations for larger, less immediate adaptations in the use of the OUD-CDS that can then be tested in subsequent interviews with key informants.

13.3.2 PCP Survey Data Analysis

PCP survey analyses will compare providers' pre- and post-implementation reports of confidence in treating patients with OUD and other items included in both PCP surveys; and to assess intervention providers' post-implementation ratings of satisfaction and acceptability of the OUD-CDS. Generalized linear mixed models will compare pre-post PCP ratings to account for repeated survey measures from PCPs and to ensure all PCP ratings are included in the estimated changes in ratings. Changes in PCP ratings may vary as a function of contextual factors or PCP characteristics. In secondary analyses of the PCP ratings, care system indicators (Site 1, Site 2, Site 3), clinic (e.g., proportion of primary care patients eligible for OUD-CDS, proportion of clinic patients with government-sponsored insurance), and provider (e.g., waiver status, number of patients eligible for OUD-CDS) characteristics may be considered as main effects or in interaction with each other or the treatment group indicator to assess their relationship with pre-post changes in survey outcomes. Provider ratings may also be used to represent provider characteristics that may modify the OUD-CDS treatment effectiveness.

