H4.1: After controlling for demographics, baseline clinical status and prior costs of care, patients with OUD or identified as high risk for OUD by the OUD-CDS will have lower healthcare costs in intervention compared to UC clinics during the observation period (i.e., savings from lower ED visits and hospitalizations will outweigh increased costs of OUD treatment and naloxone rescue kits and OUD-CDS implementation and maintenance).

Aim 5. To use mixed quantitative and qualitative methods to identify, describe and quantify barriers and facilitators to implementation of the OUD-CDS so that it can be adapted to maximize its use and effectiveness.

Secondary Analyses: As secondary outcomes, we may assess whether patients with OUD or identified as high risk for OUD by the OUD-CDS who are cared for in intervention clinics have lower post-index rates of all cause death and of fatal or non-fatal opioid overdoses during the intervention period compared to similar patients in UC clinics. We will also assess OUD-CDS use rates for intervention clinics and assess whether the effectiveness of OUD-CDS varies as a function of site, clinic, provider or patient characteristics. Finally, we will assess whether PCP ratings of confidence in treating patients with OUD differ at 9 months between treatment groups, and how intervention PCPs rate satisfaction and acceptability of the OUD-CDS tool at 9 months.

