7. Adaptation: Work with system and clinic leaders to devise and implement adaptations to the original design and workflows that address any barriers identified above and document all changes and known factors contributing to barriers and facilitators.
8. Adaptation: Make continuous recommendations to Sites 2 and 3 about their implementation plan based on findings from early implementation analysis in Site 1.
9. Follow-up PCP Surveys (9-months after go-live date): Collect 9-month surveys of all primary care clinicians in randomized clinics to assess change in confidence assessing, diagnosing, treating, and referring patients with OUD. Include set of questions about the usability, accuracy, likelihood to recommend the tool, and barriers and facilitators identified through the clinician interviews for PCPs in OUD-CDS randomized clinics.

The above series of activities will be repeated at each site. Data collected will be analyzed rapidly and any adjustments to the intervention needed to optimize the uptake of the intervention will be made and applied to subsequent sites.

Subject Recruitment and Data Collection

A. PCP Surveys

All PCPs in intervention and control randomized clinics will be surveyed at Baseline and 9 months to assess change over time in PCP's perceived ability to appropriately assess, diagnose, treat, and refer patients with OUD and their satisfaction with the OUDS-CDS. Baseline surveys will be conducted in the 1-2 months prior to intervention going live in each care system. A vanguard phase for each care system will occur approximately 2 months prior to each care system's official go-live date to pilot the roll-out of the baseline surveys and go-live procedures in a select subset of clinics. Follow-up surveys will be conducted after the intervention has been live for 9 months in each system.

For PCPs in intervention-randomized clinics, the 9-month surveys will also include a portion regarding barriers and facilitators to use of the OUD-CDS tool itself. Questions assessing the use of the tool in the 9-month survey will be designed by the study team based on findings during the early implementation phase from the quantitative monitoring data and qualitative interview data. This section of questions will help quantify barriers and facilitators to PCP use of the OUD-CDS.

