13.1.2 Primary and Secondary Outcomes (Endpoints)

Primary outcome measures will include:

1. OUD diagnosis (in the problem list or as an ICD-10 visit code) within 30 days of index visit for patients identified by the OUD-CDS as being at high risk of OU
2. Naloxone prescription within 30 days of index visit for patients with OUD or identified by the OUD-CDS as being at high risk for OUD
3. MOUD orders or referral to OUD treatment within 30 days of index visit for patients with OUD or identified by the OUD-CDS as being at high risk for OUD
4. Total days covered by an MOUD prescription in the 90 days after index visit for patients with OUD or identified by the OUD-CDS as being at high risk for OUD

Secondary outcome measures will include:

1. OUD diagnosis (in the problem list or as an ICD-10 visit code) at index or within 90 days of index visit for patients identified by the OUD-CDS as being at high risk of OUD
2. Naloxone prescription at index or within 90 days of index visit for patients with OUD or identified by the OUD-CDS as being at high risk for OUD
3. MOUD orders or referral to OUD treatment at index or within 90 days of index visit for patients with OUD or identified by the OUD-CDS as being at high risk for OUD
4. Number of ED visits during the observation period for patients with OUD or identified by the OUD-CDS as being at high risk for OUD
5. Number of hospitalizations during the observation period for patients with OUD or identified by the OUD-CDS as being at high risk for OUD
6. Healthcare costs during the observation period for patients with OUD or identified by the OUD-CDS as being at high risk for OUD, compared with healthcare costs over the same interval preceding the observation period
7. Cost of OUD-CDS implementation and maintenance
8. All-cause mortality rates during the observation period for patients at high risk of OUD
9. Fatal and non-fatal opioid overdoses during the observation period for patients at high risk of OUD
10. Rates of OUD-CDS use in intervention clinics
11. PCP ratings of confidence in treating patients with OUD prior to go-live date and 9-months following go-live date
12. Intervention clinic PCP ratings of satisfaction and acceptability of the OUD-CDS at 9 months following go-live date

Exploratory outcome measures may include:

1. Number of non-waivered PCPs becoming buprenorphine waived during the intervention period, assessed via health system administrative data

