13.3 Statistical Methods for Primary and Secondary Outcomes

This section provides an overview of the statistical methods to be employed in testing the primary and secondary outcomes. A more detailed description of the analysis may be found in the Statistical Analysis Plan. The Statistical Analysis Plan will provide more clarity about the underlying assumptions and methodological decisions regarding primary outcome analyses, including the extent to which either supplement alters the treatment effect.

Hypotheses for Aims 1 and 2 predict that the OUD-CDS intervention will increase the likelihood that patients at high risk of OUD are diagnosed with OUD (H1.1); and that among those at high risk or diagnosed with OUD it will increase the likelihoods that a naloxone rescue kit is ordered (H1.2) and that MOUD is ordered or the patient is referred to a provider who can order MOUD (H2.1), and the number of days covered by an MOUD prescription (H2.2). The hypotheses from Aims 1 and 2 will be tested using generalized linear mixed models so that the likelihood or counts of outcomes may be accurately estimated among OUD-CDS relative to UC clinics, accounting for the clustering of patients within randomized clinics. Binary outcomes (H1.1, H1.2, H2.1) will be normalized using a logistic-Normal link function, while it is anticipated that the count outcome (H2.2) will be normalized using a Poisson-Normal link function. The model will estimate fixed effects of OUD-CDS, care system and other covariates on outcomes, and random intercepts for clinics and patients (H1.1, H1.2, H2.1) or for clinics (H2.2).

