13.3.3 Patient Survey Data Analysis

Patient survey analyses will be descriptive to assess the extent to which themes identified in patient interviews are confirmed in a larger sample, and to identify correlates between these themes and other patient characteristics, such as racial/ethnic group, age group, or being at high risk for OUD vs. having diagnosed OUD.

Secondary outcomes analyses will follow the same logic as the primary outcomes analyses. Secondary outcomes that quantify person-based outcomes (e.g., MOUD maintenance and adherence) will be analyzed using generalized linear mixed models while those that represent population-averaged event rates (e.g., all-cause death rates, fatal and non-fatal opioid overdose rates) will be analyzed using generalized estimating equations.

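### Section 13.3.2 names neither the between-arm contrast nor a clinic-level term for the PCP confidence ratings, and should be reconciled with sections 2.1, 13.3 and 13.3.3

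*Combined protocol and SAP*

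**What the plan says.** The question is comparative. The secondary-analyses paragraph of section 2.1 says "we will assess whether PCP ratings of confidence in treating patients with OUD differ at 9 months between treatment groups". Section 13.1.2 lists the ratings as secondary outcome 11: "PCP ratings of confidence in treating patients with OUD prior to go-live date and 9-months following go-live date". Section 11.2 provides data from both arms: "All PCPs in intervention and control randomized clinics will be surveyed at Baseline and 9 months".

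Section 13.3.2 is the only analysis text specific to these surveys. Its model sentence reads "Generalized linear mixed models will compare pre-post PCP ratings to account for repeated survey measures from PCPs". The treatment indicator appears once, in a later sentence on further secondary analyses, where system, clinic and provider "characteristics may be considered as main effects or in interaction with each other or the treatment group indicator". No clinic random effect is mentioned.

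For the Aim 1 and 2 outcomes, section 13.3 is explicit. The models are fitted "accounting for the clustering of patients within randomized clinics", and "The model will estimate fixed effects of OUD-CDS, care system and other covariates on outcomes, and random intercepts for clinics and patients" (clinics only for days covered).

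Section 13.3.3, headed as patient survey analysis, ends with a paragraph that opens "Secondary outcomes analyses will follow the same logic as the primary outcomes analyses".

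**The concern.** Two things are missing from section 13.3.2 as written.

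The first is the contrast. A pre-post change among PCPs mixes any effect of the tool with everything else that changed over the 9 months. The protocol itself names candidates: possible waiver incentives in both arms (sections 2.2 and 10.7), and a clinician-randomised stigma intervention for PCPs at HealthPartners (section 2.1, notes). Only the comparison with usual-care clinics removes influences common to both arms.

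The second is the unit of randomisation. PCPs in one clinic share their allocation. Section 13.1.4 expects clinicians within a clinic to discuss care with each other, section 12.1 describes training at clinic meetings, and section 8.5 sends ranked use reports to the leaders of intervention clinics. Ratings, and changes in ratings, may therefore be correlated within clinic. If so, an arm comparison that models only repeated surveys within a PCP gives standard errors that are too small.

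At stake is whether a reported effect on PCP confidence is a randomised comparison with the stated error rate.

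**Working it through.** **Plan's own figures.** The documents give no sample size, power or effect size for the PCP survey, so there is nothing to reproduce directly. As a side check, Table 3 (30 clinics of 50 patients, ICC 0.03) gives detectable rates of 11.35% against 5% and 18.12% against 10%. A two-proportion calculation with design effect 1 + 49 × 0.03 = 2.47 and t critical values on 28 df gives 11.42-11.48% and 18.14-18.20%. The protocol therefore does allow for clinic clustering in its patient outcomes.

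**Inputs for PCP ratings**
- Clinics: at least 30, randomised 1:1 within system (sections 2.2 and 13.2.1).
- PCPs per clinic, m: the minimum is 3 full-time PCPs (section 8.1). Actual numbers are not given; 3 to 15 is assumed.
- Clinic ICC: section 13.2.2.1 uses 0.01, 0.03 and 0.05 for patient process measures. None is given for PCP ratings; 0.01 to 0.05 is borrowed, with 0.10 as a stress case.
- Two-sided 5% test, as for the main hypotheses (section 13.4).

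**9-month arm comparison without clinic.** With DEFF = 1 + (m − 1) × ICC, the true type I error is 2 × [1 − Φ(1.96/√DEFF)].
- m = 3, ICC 0.05: DEFF = 1 + 2 × 0.05 = 1.10; 1.96/√1.10 = 1.87; error 6.2%.
- m = 10, ICC 0.05: DEFF = 1 + 9 × 0.05 = 1.45; 1.96/√1.45 = 1.63; error 10.4%.
- m = 15, ICC 0.05: DEFF = 1 + 14 × 0.05 = 1.70; 1.96/√1.70 = 1.50; error 13.3%.

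| PCPs per clinic | ICC 0.01 | ICC 0.03 | ICC 0.05 | ICC 0.10 |
|---|---|---|---|---|
| 3 | 5.2% | 5.7% | 6.2% | 7.4% |
| 8 | 5.8% | 7.5% | 9.2% | 13.3% |
| 10 | 6.0% | 8.2% | 10.4% | 15.5% |
| 15 | 6.6% | 10.0% | 13.3% | 20.6% |

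**Simulation of the competing contrasts.** Assumptions: 30 clinics, 2,000 replicates, a continuous rating with total variance 1, both surveys answered by every PCP, no intervention effect, and a 0.3 SD shift over time in both arms. Clinic variance is 0.03-0.05 of the total, with clinic-by-time variance of 0, 0.02 or 0.05. Entries are rejection rates at nominal 5%.

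| Test | 3 PCPs | 8 PCPs | 12 PCPs |
|---|---|---|---|
| Pre-post within intervention PCPs | 43-47% | 82-86% | 90-96% |
| Arm-by-time, no clinic term, clinic effect stable | 4.4% | 5.6% | 5.0% |
| Arm-by-time, no clinic term, clinic-by-time variance 0.02 | 5.6% | 7.8% | 10.3% |
| Arm-by-time, no clinic term, clinic-by-time variance 0.05 | 6.5% | 12.8% | 15.2% |
| Arm-by-time, clinic-level analysis | 4.4-4.8% | 4.8-5.4% | 5.2-6.0% |

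The first row shows that a pre-post test responds to the time shift, not to the tool. The next three show that a stable clinic effect cancels out of change, so arm-by-time is inflated only if clinics drift differently. The last row shows that a clinic-level analysis stays close to nominal.

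**The case against.** The strongest reply is that section 13.3.2 is silent on clinic, which is different from excluding it. PCP confidence is a listed secondary outcome. The closing paragraph of section 13.3.3 goes on to treatment adherence, deaths and overdoses, which are not survey data, so it looks like a general rule placed under the wrong heading. Read with section 13.3, it would bring in a fixed OUD-CDS effect and clinic random intercepts. Section 13.3.2 also presupposes a treatment indicator for moderators to interact with, and a pre-post mixed model with an arm-by-time term is a valid between-arm analysis. Section 13.3 calls itself an overview and defers detail to a Statistical Analysis Plan.

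Much of this stands. A reader might infer that the plan ignores clinic, pools the arms, and so cannot answer its own question. The documents do not support that: no sentence excludes clinic or says that arms are pooled. A reader might also infer that inflation of 10% or more is established. It is not. Those figures need 10-15 PCPs per clinic and an ICC borrowed from patient measures, they apply to a cross-sectional comparison, and they shrink to 5.2-6.2% at the only documented clinic size.

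The gap itself remains. The general rule follows a patient-survey paragraph, its examples are patient outcomes, and the primary logic it points to concerns patients within clinics. It does not clearly replace the different comparison and clustering that section 13.3.2 spells out for PCPs. The further clarity that section 13.3 promises is about the primary outcome analyses.

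**Conclusion.** This is a specification gap in one secondary outcome. Followed as written, section 13.3.2 would yield a pre-post comparison clustered only by PCP. It would not yield the between-arm difference at 9 months that section 2.1 promises, with the clinic as the randomised unit. Sections 13.3 and 13.3.3 may be intended to fill the gap, but their application to PCP ratings is not explicit.

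That a pre-post change alone cannot be attributed to the OUD-CDS holds without any numerical assumption. The size of the clustering problem is conditional: about 5.2-6.2% true type I error with 3 PCPs per clinic over ICCs of 0.01-0.05, and about 10-13% with 10-15 PCPs at an ICC of 0.05. An arm-by-time test without clinic is inflated only to the extent that clinic effects change over time. The primary analyses are unaffected.

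**What to change.** In section 13.3.2, state the between-arm contrast as the test for PCP confidence. Either a baseline-adjusted difference at 9 months, which matches section 2.1 most directly, or arm-by-time change is defensible; choose one in advance. Fit arm, time, arm-by-time and care system as fixed effects, with random effects for PCP and for clinic, including a clinic-by-time term, and use clinic-based degrees of freedom. An analysis of clinic-level summaries is an acceptable alternative. A clinic intercept alone does not protect the arm-by-time test. Add a sentence to section 13.3.3, or move its general rule, so that its scope over PCP ratings is clear.

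The change is to wording only and needs no new data. The cost is wider confidence intervals. Relative to a 9-month comparison without clinic, the factor is √DEFF: √1.10 = 1.05, or about 5% wider, with 3 PCPs per clinic at an ICC of 0.05, and √1.70 = 1.30, or about 30% wider, with 15. Using clinic-based degrees of freedom adds a little more.

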13.3.3 Patient Survey Data Analysis

Patient survey analyses will be descriptive to assess the extent to which themes identified in patient interviews are confirmed in a larger sample, and to identify correlates between these themes and other patient characteristics, such as racial/ethnic group, age group, or being at high risk for OUD vs. having diagnosed OUD.

Secondary outcomes analyses will follow the same logic as the primary outcomes analyses. Secondary outcomes that quantify person-based outcomes (e.g., MOUD maintenance and adherence) will be analyzed using generalized linear mixed models while those that represent population-averaged event rates (e.g., all-cause death rates, fatal and non-fatal opioid overdose rates) will be analyzed using generalized estimating equations.

13.4 Significance Testing

The H1.1, H1.2 and H2.1 outcomes will be assessed 3 times for each patient – at the index visit (0 days), and 30 (for primary outcomes) and 90 days post-index. Outcomes that occur at an index visit will be coded as also having occurred by days 30 and 90. Similarly, outcomes that occur between days 1 and 30 will be coded as having occurred by days 30 and 90; and those occurring

between days 31 and 90 will be coded as having occurred by day 90. We expect that the documented actions that providers take will be overwhelmingly attributable to the index visit. Some actions that providers initiate at the index visit, such as placing a treatment referral order, may not be complete until considerations related to safety or availability are addressed. The primary outcome for H1.1, H1.2 and H2.1 will be assessed at 30 days so that these actions, likely initiated at the index visit, may be completed prior to assessing the outcome. It is possible that outcomes will not be documented for patients who have post-index visits within 90 days at non-participating clinics. We assume that these eventualities will be rare and equally likely across treatment groups.

Because virtually all of the information pertinent to the H1.1, H1.2 and H2.1 outcomes will be captured by the day 30 measure, the primary hypothesis test for these models will compare the likelihood of the day 30 outcome by treatment group. The primary hypothesis test for the H2.2 outcome will compare the likelihood of the day 90 outcome by treatment group. These comparisons will be evaluated using a two-sided test with a Type I error rate of 5%. Comparisons at other time points will aid understanding of how relative differences in OUD-CDS versus UC settings may increase or decrease in the short term. For example, OUD-CDS might initiate a course of provider actions that otherwise would not occur (increase) or merely hasten action that eventually takes place in UC settings (decrease).

The Aim 3 outcomes represent counts of events that accrue over the post-index observation periods. The event rates in OUD-CDS versus UC clinics will be evaluated using a two-sided test with a Type I error rate of 5%.

For Aim 4, Hypothesis 4.1, the marginal effect of being assigned to an intervention clinic will provide an estimate of the incremental medical cost associated with the OUD-CDS intervention. Analyses will be 2-sided, and p-values of less than .05 will be considered statistically significant. Confidence intervals will be estimated using heteroscedasticity-robust estimation methods.[55]

There are several secondary outcomes; however, multiple comparisons will not be adjusted for since these are not part of the study's primary objective.

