Aim 4. To describe and quantify costs of OUD-CDS implementation and maintenance and the short-term cost impacts of the OUD-CDS.

H4.1: After controlling for demographics, baseline clinical status and prior costs of care, patients with OUD or identified as high risk for OUD by the OUD-CDS will have lower healthcare costs in intervention compared to UC clinics during the observation period (i.e., savings from lower ED visits and hospitalizations will outweigh increased costs of OUD treatment and naloxone rescue kits and OUD-CDS implementation and maintenance).

Aim 5. To use mixed quantitative and qualitative methods to identify, describe and quantify barriers and facilitators to implementation of the OUD-CDS so that it can be adapted to maximize its use and effectiveness.

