Hypotheses for Aim 3 predict fewer ED visits (H3.1) and inpatient stays (H3.2) during the observation period of patients receiving care in the OUD-CDS relative to UC clinics. The rate at which each of these outcomes occurs per patient-year will be compared across clinics using generalized estimating equations. Clinic-aggregated counts of ED visits and inpatient stays will be normalized using a Poisson-Normal link function, and the intercept offset by the log of patient-years within the clinic. The model will estimate fixed effects of OUD-CDS, care system and other covariates on the rate of each outcome per patient-year. Should it be feasible, we will also collect and count ED visits and inpatient stays that occurred in the year prior to each patient’s index visit so that treatment group differences in pre-post changes in event rates can be quantified (i.e., treatment by time interaction).

Hypotheses for Aim 4 predict lower healthcare costs and the identification and mitigation of barriers and identification of facilitators to OUD-CDS implementation and uptake. **Analysis of costs** for this aim will include delivery costs of the OUD-CDS and incremental medical care costs attributable to the intervention, defined from the health system perspective. Intervention costs may include resources used for implementation, maintenance, compensation, and PCP and staff training – which may be assessed by interviews/surveys with implementation site staff or study resource use documentation, as appropriate – but will exclude research, development, and measurement costs, using standard micro-cost accounting methods and nationally-representative pricing of inputs. Medical care costs will include all prescribed medications and clinical inpatient, emergency, outpatient, and skilled nursing facility services incurred in the pre- and post-index observation periods by participants in each study group, as indicated by insurance claims and clinical encounter data. The study sample for the cost analysis will be participants who have continuous insurance coverage during the study period, including pharmacy benefits. This sample

will be compared to patients without continuous insurance coverage to assess representativeness and comparative completeness of utilization measurement in comparison to all study participants.

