Paid amounts for medical claims that are specific to medical groups and insurance plans may provide a biased view of costs between pre- and post-intervention periods. To address this, claims will be converted to dollar amounts using Total Care Relative Resource Values™ (TCRRVs), which are a nationally standardized set of measures that have been endorsed by the National Quality Forum[50] and are derived from Centers for Medicare and Medicaid Services (CMS) relative value units (RVUs). TCRRVs extend CMS RVU measures to include utilization categories, such as laboratory services and medications, which do not have CMS RVU weights.[51] Inpatient costs are calculated by applying TCRRVs to the diagnosis-related group classification and length of stay of the hospitalization.

Standard health econometric and specification testing methods will be used to assess the incremental differences in healthcare costs between study groups [1, 2, 39]. Specifically, healthcare care costs will be analyzed using a generalized hierarchical model with a time x study group interaction term that can account for clinic-level clustering and the correlation in each subjects' repeated measures of costs over time (i.e., pre-index and post-index). Demographics and baseline clinical status will be controlled for based on randomization imbalances and model fit criteria. The marginal effect of being assigned to an intervention clinic will provide an estimate of the incremental medical cost associated with the OUD-CDS intervention. To account for the non-normality in costs, the distribution family will be specified appropriately, such as by using the modified Park test,[2] and the goodness of fit for the specified link function will be tested, such as by using modified Hosmer and Lemeshow and Pregibon link tests.[53, 54] Confidence intervals will be estimated using heteroscedasticity-robust estimation methods.[55]

Mixed method data analysis for Aim 5 will occur rapidly as data are collected, so that new information can support decision making about revisions in the implementation plan and adaptations as the study proceeds. All data analysis and subsequent conclusions and decisions made during live implementation will be carefully documented.

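### H4.1 claims a saving net of OUD-CDS implementation and maintenance costs, but its stated test covers medical care cost only and no step adds the delivery cost

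*Combined protocol and SAP*

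**What the plan says.** **The hypothesis.** H4.1 appears in sections 2.1, 5.1 and 13.1.1. It predicts lower healthcare costs in intervention clinics and explains in parentheses what that means: "savings from lower ED visits and hospitalizations will outweigh increased costs of OUD treatment and naloxone rescue kits and OUD-CDS implementation and maintenance".

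**The test.** Section 13.4 names Hypothesis 4.1 and assigns it the marginal effect of being in an intervention clinic, which "will provide an estimate of the incremental medical cost associated with the OUD-CDS intervention". The decision rule follows: "Analyses will be 2-sided, and p-values of less than .05 will be considered statistically significant". Section 13.3 describes the same quantity: healthcare "costs will be analyzed using a generalized hierarchical model with a time x study group interaction term", fitted to each patient's pre-index and post-index costs.

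**The outcome in that model.** Section 13.3 defines it: "Medical care costs will include all prescribed medications and clinical inpatient, emergency, outpatient, and skilled nursing facility services", taken from insurance claims and encounter data.

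**Delivery cost.** Section 13.3 says the Aim 4 cost analysis "will include delivery costs of the OUD-CDS and incremental medical care costs attributable to the intervention, defined from the health system perspective". On its content: "Intervention costs may include resources used for implementation, maintenance, compensation, and PCP and staff training". It is micro-costed (sections 2.6 and 13.3), collected from site implementation staff (Table 1 in section 11.1), and listed as secondary outcome 7, separate from healthcare costs, which are outcome 6 (section 13.1.2).

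**The concern.** The hypothesis and its test concern different quantities. H4.1 is about the balance after paying for the tool. The test is about medical care cost before paying for it. If the criterion in section 13.4 is applied as written, H4.1 can be declared supported when the medical saving is real but smaller than what it cost to deliver the tool.

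This matters because the trial is meant to prepare for scaling up and dissemination (section 2.1), and the cost analysis takes the health system's perspective (section 13.3). An adopting system will want to know whether the tool pays for itself, and that is the part of H4.1 that the test leaves out.

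**Working it through.** The plan gives no power, target difference, standard deviation or per-patient delivery cost for H4.1. The power analysis in section 13.2.2.1 covers only Aims 1 and 2. There is therefore no stated figure to reproduce, and the main check is textual.

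**Step 1. Match each term of H4.1 to the tested quantity.**

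| Term in H4.1 | Inside medical care cost (13.3)? | In the tested contrast (13.3, 13.4)? |
|---|---|---|
| ED visits, hospitalizations | Yes (emergency, inpatient) | Yes |
| OUD treatment | Yes (medications, outpatient) | Yes |
| Naloxone kits | Yes (medications) | Yes |
| OUD-CDS implementation and maintenance | No | No |

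The gap is one term, delivery cost.

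**Step 2. Look for a step that adds it.** Section 13.3 names delivery cost and medical cost as the two components of the Aim 4 analysis. The text does not allocate delivery cost per patient, set a time horizon for it, add it to the intervention arm, or give a net estimate, interval or decision rule.

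**Step 3. Illustrate the consequence.** Let c be the delivery cost per intervention patient and SE the standard error of the medical-cost contrast. Suppose the true net saving is zero, so that the true medical saving equals c. By the normal approximation, the chance that the stated test shows significantly lower cost is

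P = Φ(c/SE − 1.96).

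| c/SE | c/SE − 1.96 | P |
|---|---|---|
| 0 | −1.96 | 0.025 |
| 0.25 | −1.71 | 0.044 |
| 0.5 | −1.46 | 0.072 |
| 1 | −0.96 | 0.169 |
| 1.5 | −0.46 | 0.323 |
| 2 | 0.04 | 0.516 |
| 3 | 1.04 | 0.851 |

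A test on medical difference plus c would hold this at 0.025 throughout if c is treated as known.

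**Step 4. Which ratios might apply? Every dollar figure here is an assumption.** Section 14.3.1 expects more than 10,000 patients. With clinics split about 1:1, that is roughly 5,000 in the intervention arm.

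- Delivery cost: a total of $200,000 to $1,000,000 gives c = $200,000/5,000 = $40 to $1,000,000/5,000 = $200.
- Standard error: a per-patient cost SD of $10,000 to $30,000 with 5,000 per arm gives SE = SD × √(2/5,000) = SD × 0.02 = $200 to $600, ignoring clustering.
- Ratio: 40/600 = 0.07 up to 200/200 = 1, so P runs from about 0.029 to 0.169.
- Clustering: 15 clinics per arm means about 333 patients per clinic. An ICC of .01 gives a design effect of 1 + 332 × 0.01 = 4.3, which multiplies SE by about 2.1. The top ratio falls to 200/416 = 0.48, where P is about 0.07.

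Two further features pull in opposite directions. Pre-post modelling would lower SE and raise the ratio. Restricting the cost sample to the continuously insured would raise SE and lower it.

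**The case against.** The other side has four fair arguments.

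1. **Delivery cost is not ignored.** Section 13.3 commits the Aim 4 analysis to both components, section 2.6 describes the micro-costing, and section 6.1 and Appendix A speak of assessing cost effectiveness, which needs both. This stands. A reader might infer that the plan omits delivery cost from Aim 4 altogether, and the documents do not support that. What is missing is the step that joins the two and bases the H4.1 inference on the result.

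2. **A small saving does not pass just by being a saving.** It must also reach p < .05. This stands too. A reader might infer that any medical saving below the delivery cost meets the criterion, but only a statistically significant one does. Under the Step 4 assumptions without clustering, the smallest significant saving is 1.96 × $200 = $392 to 1.96 × $600 = $1,176, above the assumed delivery cost of $40 to $200. Chance can still carry an estimate past that threshold, which is what P measures.

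3. **The detail may be elsewhere.** Section 13.3 calls itself an overview and defers to a Statistical Analysis Plan. The text available contains no combining rule, so it cannot be said that none exists anywhere. But section 13.4 states the H4.1 test explicitly, and a rule elsewhere would leave that statement needing correction.

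4. **The consequence is modest.** Healthcare cost is a secondary outcome, the leading clause of H4.1 (lower healthcare costs) is tested properly, and both components will be reported. If c is treated as known, a reader can shift the interval by c. This limits the severity without removing the mismatch. A reader might also infer that the investigators will report a medical saving as a net saving. Nothing in the text says so. The point is that the stated criterion would allow it.

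**Conclusion.** The point holds in a limited form. The test assigned to H4.1 answers a narrower question than H4.1 asks, and the shortfall is confined to OUD-CDS implementation and maintenance cost. A significant result would support lower medical care cost. It would not by itself support the net claim.

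The size cannot be fixed from the documents, because neither the per-patient delivery cost nor the standard error of the medical-cost contrast is given. At zero true net saving, the chance of apparent support is close to the nominal 2.5% if delivery cost is small relative to that standard error, about 17% if the two are equal, and about 52% at twice the standard error. The dollar assumptions tried above give about 3% to 17%, and at most about 7% once the assumed clustering is included. These figures illustrate the mechanism and do not estimate the trial's error rate. The change should be made because H4.1 is a numbered hypothesis with its own test, but it does not touch the primary outcomes.

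**What to change.** Keep the cost model in section 13.3 unchanged. Base the H4.1 inference on

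net difference = dollar-scale marginal effect of assignment on medical cost + per-patient delivery cost.

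The plan should then state:

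- **Delivery cost:** implementation plus maintenance over a stated horizon, with a fixed list of items, since section 13.3 says only what they may include.
- **Divisor:** all intervention-arm patients. Dividing by the continuously insured cost sample alone would load the whole programme's cost onto a subset.
- **Inference:** a confidence interval for the net difference, and the criterion for supporting H4.1 applied to it.
- **Sensitivity:** the net result over a range of delivery costs, including the value at which the net saving disappears.

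The alternative is to restrict the wording of H4.1 in sections 2.1, 5.1 and 13.1.1 to medical care cost, and to report delivery cost descriptively beside it.

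Either takes a few lines and no new data, because both components are already to be collected. The net version needs a little extra analysis, and its result will be less favourable than the medical-cost result by the amount of the delivery cost.
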